- **Power analysis:** We determined sample size for a two group design with PHDD as the primary outcome at post-treatment. A recent meta-analysis comparing the effects of TOP compared to placebo on heavy drinking found an overall standardized effect size of .406 [5]. The overall effect size was determined from seven studies with effect sizes ranging from .140 to .623. To ensure adequate power we calculated a sample size for a two-sample t-test by condition. The proposed primary analysis uses PHDD measured at baseline, post-intervention, 3, and 6 months in a random-intercepts regression model; however this use of additional data should serve to increase the power. A two-tailed test would require a sample size of 192 participants to detect an effect size of .406 with 80%. This is not a feasible sample size to recruit within the study's recruitment window. Alternatively, a 1-tailed test requires a sample size of 120 to have 72% power to detect the expected effect size. A one directional test is warranted given we are interested only in the improvement of PHDD for the TOP condition compared to the placebo condition. In addition, a sample size of N = 120 provides 80% power for a two-tailed test to detect a sample size of .516, a somewhat larger effect size within the range of effect sizes pooled in the recent meta-analysis [5]. Overall, we believe a sample size of N = 120 balances three needs: (1) sufficient power to compare the study groups; (2) the reality of recruiting a sample of Veterans with AUD and PTSD; and (3) overall project cost considerations.

Aims:

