- **Primary Aim Analysis.** As stated in Aim 1, we will evaluate the efficacy of PE+TOP, as compared to PE+PLA, in percent heavy drinking days (PHDD) among Veterans with comorbid AUD/PTSD at post-treatment and 3- and 6-month follow-up. The statistical model will be a generalized linear mixed model with a log link and gamma distribution variance function. If the over-dispersion parameter is close to zero a Poisson regression model will also provide equivalent model fit. The model will include a factor for treatment condition (PE+TOP, PE+PLA) and a linear term for time (baseline, post-treatment, 3, and 6 month follow-up). This model can be expanded to determine an adjusted intervention effect by including covariates such as gender and era of service. The primary test of treatment effect will be a group x time interaction. This flexible analytic method provides maximum likelihood parameter estimates based on all of the available data, allowing for the inclusion of cases with missing data and the modeling of the covariance error structure of the data across the

assessment points [90]. If the extent of missing data is small and the data appear to be consistent with a missing-at-random model, we will also carry out maximum-likelihood based on a “completer-analysis” using the observed data.

- **Secondary Aim Analyses.** As stated in Aims 2 and 3, veterans in PE+TOP, compared to PE+PLA, will show greater improvements in PTSD, depression symptoms, functional impairment and quality of life at post-treatment and 3- and 6-month follow-up. We will first examine the relationships among these outcomes to determine if composite scores should be created from highly correlated variables. This will help to reduce the number of statistical tests. The statistical model for these analyses will be random effects regression models as described in the primary aim analysis section, using identity link for Gaussian distributed linear variables and log or logit link functions for discrete or skewed outcome variables. These analyses would be in an intent-to-treat framework using maximum likelihood as before.

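### The primary model is described as random-intercepts and no covariance structure is fixed, so the standard error of the group x time test can be too small under plausible correlation patterns

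*Combined protocol and SAP*

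**What the plan says.** All the relevant text is in Section 9 of the protocol, under Statistical Considerations.

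- **Power analysis:** "The proposed primary analysis uses PHDD measured at baseline, post-intervention, 3, and 6 months in a random-intercepts regression model". This is the only place where a random effect is named for the primary model.
- **Primary Aim Analysis, family:** "The statistical model will be a generalized linear mixed model with a log link and gamma distribution variance function". The fixed effects are treatment condition and "a linear term for time (baseline, post-treatment, 3, and 6 month follow-up").
- **Primary Aim Analysis, test:** "The primary test of treatment effect will be a group x time interaction". With linear time, this is the between-arm difference in slope.
- **Primary Aim Analysis, covariance:** among the advantages of the method it lists "the modeling of the covariance error structure of the data across the" assessment points. It names no structure.
- **Secondary Aim Analyses:** "The statistical model for these analyses will be random effects regression models as described in the primary aim analysis section".

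No random slope, residual covariance structure or robust standard error is specified, and no significance level is stated for the primary test.

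**The concern.** A random intercept gives every pair of visits the same covariance and lets no participant have an individual rate of change. The primary test asks whether rates of change differ between arms. Its yardstick should therefore include how much rates of change vary between people, and a random-intercept model leaves that component out.

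Equal correlation is doubtful here. The visits span 16 weeks of treatment plus 6 months of follow-up. Baseline is a pre-treatment period selected for heavy drinking (Section 10, inclusion criterion 5), whereas the other three visits all follow treatment. If correlation falls with time, or people change at different speeds, the interval for the primary effect is too narrow and an ineffective drug is declared effective more often than planned. The plan already argues for a one-directional test, so an understated standard error would further weaken a positive claim.

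**Working it through.** **The plan's own figures, to infer alpha.** The Power analysis paragraph "found an overall standardized effect size of .406 [5"] and reports that "a 1-tailed test requires a sample size of 120 to have 72% power to detect the expected effect size". With alpha 0.05 and the normal approximation:

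- Two-tailed, 80% power: n per arm = 2(1.960 + 0.842)² / 0.406² = 95.2, rounded up to 96, so N = 192.
- One-tailed, 60 per arm: 0.406 x √30 - 1.645 = 0.579, so power = 71.9%.
- Two-tailed, d = 0.516: 0.516 x √30 - 1.960 = 0.866, so power = 80.7%.

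All three stated figures (192, 72%, 0.516 at 80%) reproduce, so 5% is a fair inference. They come from a two-sample t-test and do not involve the mixed model.

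**Formula.** Take a linear scale, complete data and four visits. Let x be centred time, Sxx = Σx², and S the true covariance of one person's four values.

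- True variance of a person's slope: x'Sx / Sxx².
- Variance used by a random-intercept model: s² / Sxx. With unit variances, s² = 1 - (average pairwise correlation).
- Ratio R = true / model. One-sided type I error = P(Z > 1.645/√R); two-sided = 2P(Z > 1.960/√R). The number per arm cancels.

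**Worked case, AR(1) 0.5, times 0, 1, 2, 3.** x = (-1.5, -0.5, 0.5, 1.5) and Sxx = 5.

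- x'Sx = 5 + 2[0.5(1.25) + 0.25(-1.5) + 0.125(-2.25)] = 4.9375, so the true variance is 4.9375/25 = 0.1975.
- Average correlation = (3 x 0.5 + 2 x 0.25 + 0.125)/6 = 0.354, so s² = 0.646 and the model variance is 0.1292.
- R = 0.1975/0.1292 = 1.53. One-sided error is 9.2%; two-sided is 11.3%.

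**Shared early drop.** Suppose both arms fall 1 SD by post-treatment and then stay flat. A straight line misses those means by a sum of squares of 0.30, which adds 0.30/3 = 0.10 to s². Then R = 0.1975/(0.746/5) = 1.32 and the one-sided error is 7.6%.

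**Range.** All correlations, SDs and drops are assumptions; the documents give none. Ranges cover times coded 0-3 and months 0, 4, 7, 10, with AR(1) decay per visit.

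| Assumed pattern | R | One-sided | Two-sided | One-sided, shared 1 SD drop |
|---|---|---|---|---|
| Equal correlation 0.5 | 1.00 | 5.0% | 5.0% | 3.6-3.8% |
| AR(1) 0.5 | 1.52-1.53 | 9.1-9.2% | 11.2-11.3% | 7.6-7.8% |
| AR(1) 0.7 | 1.73-1.74 | 10.5-10.6% | 13.6-13.7% | 8.3-8.6% |
| AR(1) 0.8 | 1.83-1.84 | 11.2-11.3% | 14.7-14.9% | 8.1-8.5% |
| Own slopes, slope variance at last visit = residual variance | 1.31 | about 7.6% | 8.7% | about 6% |
| Baseline to follow-up 0.3, between follow-ups 0.7 | 1.32-1.41 | 7.6-8.3% | 8.8-9.8% | 5.8-6.7% |
| Baseline to follow-up 0.5, between follow-ups 0.6 | 1.09-1.11 | 5.8-5.9% | 6.0-6.3% | 4.1-4.5% |
| Equal correlation 0.5, baseline SD 0.6 of later SD | 0.86-0.89 | 3.8-4.1% | 3.5-3.8% | 2.7% |

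**Simulation, Gaussian (20,000 trials per case, two-sided, no drop).** The random-intercept test rejected in 5.0% (equal correlation), 11.0% (AR(1) 0.5), 14.0% (AR(1) 0.7) and 8.9% (own slopes). With the error taken from participants' own slopes, the rate was 4.6-5.3% in every case, with or without the drop.

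**Simulation, gamma log-link random-intercept model (600 trials per case, Monte Carlo error about 1 point).**

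| True structure | Two-sided | One-sided |
|---|---|---|
| Random intercept | 4.3% | 5.7% |
| Slope SD 0.15 (log scale) | 8.0% | 5.7% |
| Slope SD 0.30 (log scale) | 13.7% | 9.3% |
| AR(1) random effect 0.5 | 9.3% | 10.0% |
| AR(1) random effect 0.8 | 7.8% | 8.2% |

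**Categorical time is not a cure by itself.** For post-treatment minus baseline, with correlations 0.4 (baseline to follow-up) and 0.7 (between follow-ups), the ratio is (1 - 0.40)/(1 - 0.55) = 0.60/0.45 = 1.33.

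**The case against.** Four points can be made for the plan.

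1. **Random intercepts only is not settled.** The term appears once, in a clause defending the t-test calculation. The analysis paragraph speaks of modelling the covariance. This stands: a reader might infer that the plan commits to intercepts and nothing else, and the text does not go that far. But the covariance remark describes what the method allows and chooses nothing. Either the random-intercepts label governs, or the structure can be picked after the data are seen.
2. **The direction is not fixed.** A reader might infer that the standard error is too small whenever visits are not equally correlated. That is false. A smaller baseline SD gives 3.5-3.8% two-sided. Other conservative patterns are a larger SD at the middle visits (2.6%) and first and last visits correlated more than adjacent ones (about 1.7%). Selecting for heavy drinking could itself narrow the baseline spread.
3. **A shared early drop offsets inflation.** Both arms receive PE and medical management counselling, so such a drop is plausible. It removes most of the excess when baseline is only less correlated than the follow-ups are with each other. Under AR(1) it leaves about 8-9% one-sided. The 1 SD drop is itself an assumption.
4. **Aims 2 and 3.** A reader might infer that their p-values are also too optimistic. The secondary paragraph points back to the Primary Aim Analysis section, which never says random intercepts. Only a possible effect is supported.

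**Conclusion.** The concern holds in a conditional form, as a should-fix. The plan calls the primary model random-intercepts, tests a difference in slopes, and specifies no safeguard for the standard error. If the label is followed, the type I error of a nominal 5% test is:

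- about 9-11% one-sided (11-15% two-sided) under AR(1) correlation of 0.5 to 0.8, or about 8-9% one-sided with a shared 1 SD early drop;
- about 6-8% one-sided with baseline-to-follow-up correlation 0.3-0.5 and follow-up correlation 0.6-0.7, or about 4-7% with the drop;
- below 5% under some other patterns.

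These figures rest on a linear-scale derivation, assumed correlations and an inferred 5% level. The gamma simulations agree in direction but not in every one-sided case. The documents do not support saying that the primary result will be too optimistic, only that it may be and that nothing in the plan prevents it. N = 192, 72% power and d = 0.516 are unaffected.

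**What to change.** In the Power analysis and Primary Aim Analysis paragraphs, replace the random-intercepts description with a pre-specified analysis that does not rely on equal correlation:

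- **Gaussian outcomes (Aims 2 and 3):** unstructured covariance across the four visits. That is 4 variances + 6 covariances = 10 parameters, feasible with 120 participants.
- **PHDD:** a robust (sandwich) standard error with a small-sample correction, and a random slope alongside the random intercept if the model converges.
- **Fallback:** random intercept with the robust standard error, with the convergence rule written down before unblinding.
- State the alpha and sidedness of the primary test in the same paragraph.

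The cost is SAP wording: no new data and no change to sample size or conduct. Intervals will be somewhat wider under some patterns, and the fallback covers occasional convergence failures. If equal correlation does hold, little is lost.

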***Please add a Study Contact**

[name]
[name]

The Study Contact(s) will receive all important system notifications along with the Principal Investigator. (e.g. The project contact(s) are typically either the Study Coordinator or the Principal Investigator themselves).

VASDHS - IRB Protocol

v20150312

Section 1 - Preliminaries

Principal Investigator:

[name]

Protocol Title:

Combining Topiramate and Prolonged Exposure for PTSD and Alcohol Use Disorder

IRB Protocol Number:

H170056

Protocol Nickname:

TOP Study

Form Template Version:

v20150115

Date Prepared:

10/04/2023

1a) Is this study considered human research?

Yes No

1b) Is this a request for a determination of exemption from IRB review?

Yes No

1c) Is this a request for an expedited IRB review?

Yes No

Section 1.3 New Protocol or Transfer/Renewal of Prior Protocol

1.3) Select the type of protocol application:

1.3a) Is this a new protocol? (if transfer to VA IRB, select **No)**

Yes No

1.3b) Is this a resubmission of a VASDHS IRB protocol?

Yes No

1.3c) Is this a transfer of a protocol to the VASDHS IRB?

Yes No

Section 2 - Research Subjects

2a) What is the total planned number of VASDHS-consented subjects needed?

(Include even if using a waiver of documented consent, e.g. oral consents)

120

2b) What is the total number of VASDHS subjects needed that WILL NOT be consented (e.g., retrospective reviews) ?

0

Section 2.1 Consented Subject Groups

2.1) For each of the subject categories listed below, indicate whether or not these subjects will be enrolled (consented) in the study: (exclude cases of data or specimens only)

2.1a) Children under age 18

Yes No

2.1b) Women of child-bearing potential

Yes No

2.1c) Pregnant women

Yes No

2.1d) Individuals with cognitive/decisional impairment

Yes No

2.1e) Non-English speaking individuals

Yes No

2.1f) Prisoners of War [explicitly targeting this group]

Yes No

2.1g) Non-Veterans (Note: A justification will be required below)

Yes No

2.1h) Incarcerated individuals (Note: VA CRADO approval will be required)

Yes No

2.1i) VA employees (or WOCs)

Yes No

2.1j) Students

Yes No

2.1k) Patients with cancer (or high cancer risk) [explicitly targeting this group]

Yes No

Section 3 - Study Features (these items default to "No" for convenience)

3) This section consists of several Yes/No questions addressing protocol characteristics. [Click on Save and Continue.](#)

Section 3.1 Protocol Basics

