Design. This prospective, randomized, controlled trial will assess the efficacy of PE+TOP as compared to PE+PLA. Medical providers, participants, and evaluators will be blinded to the intervention condition. TOP or placebo will be administered over 16 weeks (6 weeks of upward titration and 10 weeks at maximum target dose up to 250mg per day) of active treatment, and participants will be asked to complete 12 sessions of PE during those 16 weeks (allowing for missed appointments, which are common among individuals with AUD and PTSD). Ongoing assessments of primary outcomes (i.e., heavy drinking days, PTSD symptoms, functional impairment) will be made at baseline, post-treatment, and 3- and 6-months following treatment completion. Our hypotheses are that the combined intervention (PE+TOP) will be more effective in reducing heavy drinking events and PTSD symptoms and in improving functioning and quality of life than PE with placebo (PE+PLA) among male and female Veterans with AUD and PTSD diagnoses. One hundred twenty (120) participants will be recruited through San Diego VA addictions and mental health treatment programs and randomized at the individual level. All symptomatic and interested participants who do not receive TOP during the trial will be offered the treatment immediately after blind is broken following the final assessment. In order to ensure we are examining outcomes in a multifaceted and informative manner, we will include assessments of primary comorbid conditions and multiple domains of functioning to provide the most comprehensive and informative data to inform clinical practice with this complicated population. Biweekly self-report assessment of substance use, cravings, and PTSD and depression symptoms will be completed. We will also examine differential drop out, early response, and treatment adherence.

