If the visit is done by phone, the (1) the approved ICF, (2) the approved HIPAA document, (3) the CA Experimental Subjects Bill of Rights, and (4) baseline assessment documents will be emailed (using VA Azure RMS and the participant will need to print all documents) and/or hard copied will be mailed to the participant. Study staff will call the participant at the scheduled appointment time to complete the documents. Study staff along with the participant will complete the informed consent document, explain the HIPAA Authorization, and CA Experimental Subjects Bill of Rights. The participant will be instructed to mail back the signed consent and HIPAA forms. Once the forms are received by study staff, the baseline assessments will be scheduled and completed by phone or through VA approved secure Telehealth communication software.

Participants will be sent a copy of the signed and dated forms, regardless if the Informed Consent appointment was completed by VA approved secure Telehealth communication software or by phone.

Once documentation of written consent is received, the staff member will begin the baseline eligibility assessment. The participant may use the fillable PDF to complete the self-report forms and return them via MyHealtheVet, may read their responses to the items to a staff member who will transcribe the responses into an electronic form behind the VA firewall or docum

ent can be signed and returned via encrypted email (using VA Azure RMS). The interview-based measures will be completed and electronically transcribed. Safety concerns will be reviewed with a licensed mental health provider (e.g., suicidality). Refer to the *Risk Management* section of the protocol for telephone safety procedures.

Eligible participants will be required to complete laboratory diagnostic testing at the VA location of their choice. This is the only visit that the veteran is required to attend in person. Following laboratory diagnostic testing, the veteran will be scheduled for all remaining baseline medical and psychology meetings by telephone and/or VA approved secure Telehealth communication software.

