Following the baseline eligibility appointments, if the veteran is found to be eligible for the treatment portion of the study, they will be randomly assigned to PE + Placebo or PE + Topiramate. All psychiatry and therapy appointments will be scheduled through VA approved secure Telehealth communication software or phone. We will send an encrypted email (using VA Azure RMS), a message to MyHealthyVet, or send documents by US mail containing all therapy and psychiatry materials to be used throughout the treatment portion of the trial. The participant may use the fillable pdf's to complete the forms and return them via MyHealtheVet, may read responses to the items to a staff member who will transcribe the responses into an electronic form behind the VA firewall, or they may be returned via encrypted email (using VA Azure RMS).

Assessments will be administered again at mid-treatment, immediately after completion of the treatment portion of the study, at 3-month post-treatment, and finally at 6-month post-treatment, using phone and/or VA approved secure Telehealth communication software. We will send an encrypted email (using VA Azure RMS), a message to MyHealthyVet, and/or send documents by US mail containing assessment materials to the veteran. The veteran will submit the completed assessment materials by either returning images of the documents through MyHealtheVet, mailing back completes self-report assessments, or a staff member may read questions and responses will be transcribe into an electronic form behind the VA firewall, or they may be returned via encrypted email (using VA Azure RMS). The interview-based measures will also be completed and electronically transcribed.

Participant compensation - Vendorizing is now accepting digital signatures on all 10091 forms. Users who are registered in CEP (Customer Engagement Portal) will be able to submit vendor forms electronically. The participant may also use the fillable pdf to complete the form and return them via MyHealtheVet, they may be mailed a blank 10091 form to be mailed back to study staff for submission and payment, or they may be returned via encrypted email (using VA Azure RMS)..

Section 9.1 Clinical Procedures

9.1) Differentiate research procedures (or any procedures done for research purposes only) from clinical procedures (procedures that are done as part of standard care).

(Note: this differentiation should be clear in the consent form as well)

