10) Describe the characteristics of the proposed subject population. Include age, gender, ethnicity, and health status as appropriate. Provide inclusion and exclusion criteria as appropriate. Indicate the number of VASDHS participants to be studied. For multisite studies, also provide the total number of subjects from all sites. Indicate the estimated number of consented subjects that will fail the screening process, if any.

Protection of Human Subjects

1. Risks to the Subjects.

1.a. Human Subjects Involvement and Characteristics

The participants in this study will be 120 outpatient male and female Veterans (60 per treatment condition), ages 18 or older, with alcohol use disorder (AUD) and PTSD.

In order to ensure that our sample represents the diversity of comorbidity in Veterans with PTSD, exclusion criteria are minimized and include only those factors that contraindicate primary treatment for PTSD, prevent the Veteran from benefiting from the current program, or may interfere with the mechanisms under study.

Inclusion criteria are:

- 1) Veterans of the U.S. military and/or Reserve/National Guard members,
- 2) at least 18 years of age,
- 3) survivors of a psychological trauma meeting DSM-5 criterion A, and are at least one month post-trauma,
- 4) have current DSM-5 diagnoses of AUD and PTSD based on semi-structured diagnostic interviews,
- 5) have at least 20 days of heavy drinking (≥ 5 drinks/day for men and ≥ 4 drinks per day for women) in the last 90 days spent in a non-restricted environment and meet criteria for heavy drinking at least 4 days in the last 30 days prior to screening,
- 6) are not currently receiving trauma-focused psychotherapy,
- 7) are literate in English and intend to stay in the San Diego area during the study,
- 8) are willing to attend psychotherapy, medication, and assessment sessions,
- 9) trying or planning to try to cut down on or abstain from alcohol,
- 10) for females of childbearing potential, agree to use an approved form of contraception for the duration of the study, including hormonal contraceptives (e.g., oral contraceptives or implantable devices), intrauterine device (IUD), or double barrier methods (e.g., diaphragm with spermicidal condom); barrier method is preferred as topiramate may make birth control less effective,

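### The topiramate arm is about 74 in the genetic analysis but 60 in the design, 120 is entered as both the consented and the randomised number, and the two power figures at 120 are unlabelled complete-data t-test figures

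*Combined protocol and SAP*

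**What the plan says.** All references are to the combined protocol and SAP.

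- **Consented number.** Section 2, item 2a asks "What is the total planned number of VASDHS-consented subjects needed". The answer is 120.
- **Randomised number.** Section 9, Design: "One hundred twenty (120) participants will be recruited through San Diego VA addictions and mental health treatment programs and randomized at the individual level". Section 10, 1.a: "120 outpatient male and female Veterans (60 per treatment condition". The Recruitment paragraph of Section 9 specifies permuted blocks that equalise the arms at regular points, stratified by use of anti-relapse medication.
- **Screen failures.** The Section 10 prompt reads "Indicate the estimated number of consented subjects that will fail the screening process, if any". The answer contains no such number.
- **Primary power.** Section 9, Power analysis, uses a two-sample t-test on percent heavy drinking days (PHDD) at post-treatment. It says that "a 1-tailed test requires a sample size of 120 to have 72% power to detect the expected effect size" and that "a sample size of N = 120 provides 80% power for a two-tailed test to detect a sample size of .516" (the last words evidently mean an effect size). It expects the repeated-measures model to add power but gives no amount.
- **Missing outcomes.** The Missing Data and Primary Aim Analysis paragraphs provide for them through a likelihood analysis of all randomised cases. No rate is given.
- **Genetic analysis.** Section 9, Genetic Testing, gives about 74 participants in the topiramate arm. The genetic Power Analysis that follows uses a total N of 75.

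**The concern.** Three counts do not fit together or are not fully described.

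First, an arm of about 74 cannot come from 120 participants randomised 60 and 60. If the genetic power rests on that arm, it rests on participants the design does not provide.

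Second, 120 consented and 120 randomised can both hold only if nobody is lost between consent and randomisation. Item 2a is the consent number put to the IRB.

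Third, the two primary power figures assume a post-treatment value from every randomised participant, and the text does not say so. There is little room to spare: the plan already rejects 192 as infeasible and accepts 72% on a one-tailed test. Its power at the number actually expected to be measured should therefore be visible.

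**Working it through.** **1. Reproduce the primary figures.** Inputs from Power analysis: d = 0.406 and d = 0.516, N = 120, so n = 60 per arm. Alpha is not stated; 0.05 is assumed because it reproduces all three stated figures. The noncentrality is d × √(n/2).

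- Two-sided, 80%, d = 0.406: n = 2 × (1.960 + 0.842)² / 0.406² = 95.2, so 96 per arm, 192 in total. Stated: 192.
- One-sided, d = 0.406: 0.406 × √30 = 2.224; normal approximation Φ(2.224 − 1.645) = 71.9%; noncentral t 71.4%. Stated: 72%.
- Two-sided, d = 0.516: 0.516 × √30 = 2.826; normal approximation Φ(2.826 − 1.960) = 80.7%; noncentral t 80.0%. Stated: 80%.

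The arithmetic is right, with 60 measured per arm and no loss.

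**2. Arm size.** 74 − 60 = 14 too many. Under equal allocation, 74 per arm means 148 randomised, not 120. Within 120 it means 74:46, a difference of 28. Incomplete blocks in two strata could produce that only if each were 14 out of balance, which needs a block size of at least 28 and contradicts the stated 60 per condition.

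**3. Genetic power, if the 75 is the topiramate arm.** Two-sided t-test, d = 0.75, alpha 0.05, noncentrality 0.75 / √(1/n₁ + 1/n₂). The split between the two genotype groups is not stated, so two are shown.

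| Assumed split | About 75 | 60 |
|---|---|---|
| 25/75 | 79.6% (19:56) | 69.6% (15:45) |
| 50/50 | 88.9% (37:37) | 81.5% (30:30) |

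The 25/75 split matches the stated 0.8. At 60 with that split, the effect detectable with 80% power is d = 0.85.

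**4. Consent to randomisation.** Sections 11 and 12.1d put a screen and record review before consent. After consent, two routes of loss remain in the standard pathway. The diagnostic interview for alcohol and substance use disorder is given at baseline (Section 9.8), and Recruitment places baseline after consent. Recruitment also randomises only those who then choose to go on. No loss rate is documented. At an assumed 5% or 10%, randomising 120 needs 120/0.95 = 126.3, so 127 consents, or 120/0.90 = 133.3, so 134. If 120 were a cap on consents, 114 or 108 would be randomised.

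**5. Missing post-treatment PHDD.** The same t-test by noncentral t, with assumed rates:

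| Assumed missing | N measured | One-sided, d = 0.406 | Two-sided, d = 0.516 |
|---|---|---|---|
| 0% | 120 | 71% | 80% |
| 10% | 108 | 67% | 76% |
| 20% | 96 | 63% | 71% |
| 30% | 84 | 58% | 65% |

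**6. Possible offset.** Adjusting for a baseline value correlated r with the outcome raises the effective effect to d/√(1 − r²). The one-sided 71% is restored at r = 0.32, 0.45 and 0.55 for 10, 20 and 30% missing. For example, at N = 96: 0.406/√(1 − 0.45²) = 0.455, and 0.455 × √24 = 2.23, the noncentrality of step 1. The documents state no correlation.

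**The case against.** The sponsor can say the following, and much of it stands.

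- **Which count 120 is.** A reader might infer that this cannot be known. The documents do not support that: Design, Power analysis and Section 10 together show that 120 is the recruited and randomised target. Only item 2a attaches it to consent, and nothing says that 120 caps consents. If enrolment runs until 120 are randomised, power is untouched and one form entry needs changing.
- **When eligibility is settled.** A reader might infer that it is wholly settled after consent, from "Once documentation of written consent is received, the staff member will begin the baseline eligibility assessment" and "if the veteran is found to be eligible for the treatment portion of the study, they will be randomly assigned". Those sentences belong to temporary COVID-19 procedures. Section 12.1d books consent only after a finding of eligibility, and the laboratory tests may fall at screening or at randomisation. Final eligibility is partly, not wholly, settled after consent.
- **Dropout.** A reader might take the high treatment dropout described in Section 6 as a missing-outcome rate. It is not one. Section 9, Data Management, plans outcome collection whether or not treatment continues.
- **The wrong test.** The planned primary test is a group by time interaction over four occasions, not a t-test. The figures in step 5 are therefore not the power of the planned analysis, and the offset in step 6 shows that the net effect could be nil. This stands. It is also why the gain from repeated measures needs a number before it is relied on.
- **The genetic section is exploratory.** This is true, and the primary figures use 60 per arm. Its visits at 2, 5 and 8 months also do not match 16 weeks of treatment with 3- and 6-month follow-ups, so the text may have come from elsewhere. The 75 is called a total N and not expressly the topiramate arm, so that part stays conditional.

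**Conclusion.** The conflict between about 74 and 60 is certain. Its effect on genetic power is conditional: from about 80% to about 70% if the 75 is the topiramate arm and the genotype split is 25/75, and to about 81% under an even split.

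The double use of 120 is also certain. It makes item 2a too low by whatever number is lost after consent, and that number is not documented.

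The 72% and 80% are correct as complete-data t-test figures and should be labelled so. A reader might infer that the primary analysis is short of power by a known amount. The documents do not support that: they give no missing-outcome rate and no correlation. The ranges of 67 to 58% and 76 to 65% hold only at the assumed 10 to 30% missing, for the t-test at an inferred alpha of 0.05, before any repeated-measures gain.

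These are corrections worth making, not a flaw in the design.

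**What to change.** 1. Keep 120 as the randomised target, 60 per condition.
2. In Genetic Testing, change the topiramate arm from about 74 to 60. If the 75 in the genetic Power Analysis is that arm, restate the power at 60 with the genotype split named; if it is not, say which participants it counts.
3. In item 2a, enter a consented number above 120, and give the assumed post-consent failure rate there and in answer to the Section 10 prompt.
4. In Power analysis, label the 72% and the 80% as complete-data t-test figures and state the alpha. Then either restate both at an assumed missing post-treatment PHDD rate, or give the power of the planned group by time test with its assumed correlation and missingness.

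The cost is a minor amendment to item 2a, corrected counts in an exploratory section, and stated power that may look less favourable. The randomised target and the design do not change.
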